The subjects in this cohort can be discharged at the discretion of the investigator and will be followed up after surgery for assessment of AKI up to 7 days (AKI-SCr using SCr values from local laboratory testing and 24-hour UO to assess stage 3 AKI-UO) and for assessment of MAKE event at day 30 and day 90. Hospital and ICU stay will also be recorded. AEs and medication use will be recorded until 24 hours after T0. Urine samples will be collected for NC and biomarker assessments. If available, local laboratory test results and 24-hour UO data will be collected from medical records. No additional blood samples will be taken for study purposes after visit 2. See Schedule of Assessments below [Table 2].

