6. Safety central laboratory tests including serum creatinine (SCr) and cystatin C.
7. If the subject is discharged from hospital after day 7, the last result of SCr before discharge from local laboratory testing will be collected.
8. UO assessment: from T0 (visit 2) to T72 (visit 5) when the subject is in the ICU, UO will be recorded every 12 hours and fluid intake will be recorded every 24 hours. The eCRF should indicate when UO data have to be recorded from the subject ICU record. During the first 72 hours following surgery (i.e., visits 3 to 5), the investigator will be asked to record information on AKI-UO stages 1 to 3 in the eCRF to assess their occurrence as per investigator discretion. When the subject is discharged from the ICU, but is still in the hospital UO and fluid intake every 24 hours will be recorded up to day 7 (visit 8).
9. Include albuminuria dipstick.
10. The first dose of investigational product (IP)/study drug to be administered as soon as possible after the NC AKIRisk score is assessed between 2 and 22 hours after T0 is  $> 0.3$  (ng/mL)/1000 to allow completion of first treatment within 24 hours after T0. If the first dose of IP administration is completed within 8 hours after T0, the second dose of IP will be administered at 24 hours after T0 and the third dose of IP will be administered at 48 hours after T0. If the first dose of IP administration is completed past 8 hours after T0, the second dose of IP will be administered at 16 hours after the start of the first dose, and the third dose of IP will be administered at 40 hours after the start of the first dose of IP.  
Second and third dosing of the IP: a 2-hour treatment window before or after designated administration time is allowed.
11. Additional urine samples will be taken and stored to assess various clinical and compound related biomarkers.
12. AE will be collected from informed consent until visit 9 or until the subject is determined to be a screen failure. If the subject is discontinued from the study prior to visit 9, AEs will be collected until the EoS visit has been completed. After the end of all the procedures of visit 9 until visit 10, only serious AEs will be collected.
13. Assess data on renal replacement therapy, mortality, ICU stay, total hospital stay and duration of mechanical ventilation (time ventilation weaning, i.e., time from T0 to extubation).

*Footnotes continued on next page*

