**Table 2 Schedule of Assessments – Subjects in the Observational Cohort**

| Study Period                       | Screening         | Surgery        |                   |                 | Follow-up Period |                 |                 |                |                 |                      | Unscheduled    |
|------------------------------------|-------------------|----------------|-------------------|-----------------|------------------|-----------------|-----------------|----------------|-----------------|----------------------|----------------|
|                                    |                   | Visit Number   | 1                 | 2   | 3                | 4               | 5               | 8              | 9  | 10/EoS  |                |
| Day                                | -28               | pre            | peri  | post            | 2                | 3               | 4               | 7/DoD          | 30              | 90                   |                |
| Visit Window                       | ≥ -28 days        | -              | -                 | -               | T0 + 24 hours    | T0 + 48 hours   | T0 + 72 hours   | 4 to 7 days    | 23 to 37 days   | 83 to 97 days        |                |
| Assessment                         |                   |                |                   |                 |                  |                 |                 |                |                 |                      |                |
| Informed Consent                   | X                 |                |                   |                 |                  |                 |                 |                |                 |                      |                |
| Inclusion/exclusion criteria       | X                 |                |                   |                 |                  |                 |                 |                |                 |                      |                |
| Medical history, demographics      | X                 |                |                   |                 |                  |                 |                 |                |                 |                      |                |

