9. Local laboratory test results will be collected from medical records, including serum creatinine and serum cystatin C (if available).
10. 24-hour urinary output data will be collected from medical records (if available).
11. Subjects will only be randomized if postoperative NephroCheck® (NC) AKIRisk® score (assessed between 2 to 22 hours after T0) is  $> 0.3 \text{ (ng/mL)}^2/1000$ . If the AKIRisk score is  $\leq 0.3 \text{ (ng/mL)}^2/1000$ , the subject cannot be randomized and will be followed up in the observational arm.
12. Urine sampling only for NC and biomarker assessments if subjects are still in the intensive care unit and urine can be sampled from the catheter. Urine samples will be taken, but frozen until later assessment at the central laboratory.
13. Visit 9 and 10 may be conducted by phone if the subject is unable to visit the site and will require contact for MAKE parameters collection.
14. When an assessment of a full physical examination is available and performed within 30 days before surgery, the assessment can be used even if it was performed prior to the informed consent.

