#### **5.7.4 Subjects in the Observational Cohort**

If the NC is negative, i.e., the AKIRisk score is  $\leq 0.3$  (ng/mL) $^2/1000$  at all assessments between 2 and 22 hours after T0, the subject cannot be randomized. These subjects will be included in the observational cohort. The aim of following up the subjects in the observational cohort is to further evaluate the AKIRisk score, as well as other risk factors (including clinical characteristics and biomarkers) for AKI and MAKE. The subjects in this cohort can be discharged at the discretion of the investigator and will be followed up after surgery for assessment of AKI up to 7 days (AKI-SCr using SCr values from local laboratory testing and 24-hour UO to assess stage 3 AKI-UO) and for assessment of MAKE event at day 30 and day 90. Days 30 and 90 may be conducted by phone if the subject is unable to visit the site.

For subjects in the observational cohort, local laboratory test results of the parameters mentioned in [Table 8](#) and 24-hours UO data will be collected, if available at visits according to the Schedule of Assessments [[Table 2](#)]. Urine sampling for NC and biomarkers will be performed separately according to the Schedule of Assessments [[Table 2](#)] for posthoc analysis of study outcomes, and only if the subject has a urinary catheter to facilitate sampling. MAKE parameters, i.e., all-cause mortality, RRT and/or  $\geq 25\%$  sustained reduction in eGFR based on SCr or S-Cystatin-C will be assessed according to the Schedule of Assessments [[Table 2](#)]. AEs and medication use will be recorded until 24 hours after T0.

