**Table 8      Laboratory Test Data in the Subjects of the Observational Cohort**

| Visit               | Type                            | Test   |
|---------------------|---------------------------------|--|
| Visits 3-10/EoS     | Hematology                      | Hemoglobin
Hematocrit
Red blood cell count
Platelet count
Leukocytes   |
| Visits 3-10/EoS     | Biochemistry                    | C-reactive protein
Creatinine
eGFR (any equation)
Cystatin-C
Alkaline phosphatase
AST
ALT
Gamma-glutamyltransferase
Total bilirubin
Total protein
Albumin
CK
CK-MB |
| Visits 8, 9, 10/EoS | Urinalysis                      | Protein
Albumin   |
| Visits 3 to 5       | Biomarkers/NephroCheck® - Urine | AKIRisk® score
KIM1(Urine samples on visits 3, 4 and 5 will be stored until assessment at central lab)  |

ALT: alanine aminotransferase; AST: aspartate aminotransferase; CK: creatine kinase; CK-MB: creatine kinase-muscle/brain; EoS: end of study; KIM1: kidney injury molecule-1.

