### 6.1.2 Secondary Efficacy Endpoints

1. Proportion of subjects developing AKI (any stage) based on SCr criteria from the KDIGO guideline within 7 days after T0 (i.e., until Visit 8) (AKI-SCr7d).

[SCr evaluation visit: baseline, Visit 3, 4, 5, 6, 7 and 8 (24 hours, 48 hours, 72 hours after T0, and Day 5, 6 and 7/DoD). If the hospital discharge is earlier than Day 7, then the visits prior to DoD and Visit 8 (DoD) will be used.]

- If the subject meets at least one of the following conditions, then the subject will be treated as developing AKI-SCr7d.
  - Increasing in SCr  $\geq 0.3 \text{ mg/dL}$  within any 48 hours until Visit 8; and/or,
  - Increasing in SCr  $\geq 1.5$  times baseline until Visit 8.

2. Proportion of subjects developing AKI based on all captured criteria from the KDIGO guideline within 72 hours after T0 (AKI-KDIGO72h).

[SCr evaluation visit: baseline, Visit 3, 4 and 5 (24, 48, 72 hours after T0)]

[UO evaluation visit: Visit 3, 4, and 5 (0-12 hours, 12-24 hours, 0-24 hours, ..., and 48-60 hours, 60-72 hours and 48-72 hours after T0)]

- If the subject meets at least one of the following conditions, then the subject will be treated as developing AKI-KDIGO72h.
  - Increasing in SCr  $\geq 0.3$  mg/dL within any 48 hours until Visit 5;
  - Increasing in SCr  $\geq 1.5$  times baseline until Visit 5; and/or,
  - Urine volume  $< 0.5$  ml/kg per hour for any one of 12 consecutive hours until Visit 5 (i.e., 0-12 hours after T0, 12-24 hours after T0, ..., or 60-72 hours after T0).
- 3. Proportion of subjects developing AKI based on all criteria from the KDIGO guideline within 7 days after T0 (AKI-KDIGO7d).

[SCr evaluation visit: baseline, Visit 3, 4, 5, 6, 7 and 8(24 hours, 48 hours, 72 hours after T0, and Day 5, 6 and 7/DoD). If the hospital discharge is earlier than Day 7, then the visits prior to DoD and Visit 8 (DoD) will be used.]

[UO evaluation visit: Visit 3, 4, 5, 6, 7 and 8 (0-12 hours, 12-24 hours, 0-24 hours, ..., and 120-132 hours, 132-144 hours and 120-144 hours after T0). If the hospital discharge is earlier than Day 7, then the visits prior to DoD and Visit 8 (DoD) will be used.]

  - If the subject meets at least one of the following conditions, then the subject will be treated as developing AKI-KDIGO7d.
    - Increasing in SCr  $\geq 0.3$  mg/dL within any 48 hours until Visit 8;
    - Increasing in SCr  $\geq 1.5$  times baseline until Visit 8; and/or,

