## 7.9 Other Analyses

### 7.9.1 Analysis for Observational Cohort

[Analysis population: PFAS, Analysis group: Weighted Total (PFAS)]

Potential risk factors (demographics, subject characteristics, biomarkers) for development of AKI and MAKE (AKI-SCr72h, AKI-SCr7d, MAKE30, and MAKE90) will be explored. Population standardization is used in this analysis. Weighted Total (PFAS) is the set of NC negative group and NC positive group weighted by (the number of subjects assigned to Placebo group + the number of subjects assigned to ASP1128 group)/ (the number of subjects in Placebo group). The estimate of the unadjusted risk ratio, 2-sided 90% confidence interval, true positive rate, and true negative rate for AKI and MAKE (AKI-SCr72h, AKI-SCr7d, MAKE30, and MAKE90) proportion will be calculated by risk factors listed in [\[Table 13\]](#). In Analysis for Observational Cohort, subjects whose status of AKI and MAKE is unknown due to, say, the missing data of SCr will not be counted as AKI/MAKE event. This treatment for missing data is different from it for primary and secondary endpoints.

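### The prognostic-factor analysis scores unknown AKI/MAKE as no event, with no missing-data sensitivity analysis, although creatinine ascertainment differs between the two NephroCheck groups

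*SAP*

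**What the plan says.** The Prognostic Factor Analysis Set (PFAS) combines placebo subjects, all NephroCheck (NC) positive, with the NC-negative observational cohort. SAP 7.9.1 plans an unadjusted risk ratio (RR) with 90% interval, a true positive rate (TPR) and a true negative rate (TNR) for each factor in Table 13, with the positives up-weighted. A subject whose status is "unknown due to, say, the missing data of SCr will not be counted as AKI/MAKE event". The SAP adds that this differs from the handling of the primary and secondary endpoints.

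Creatinine (SCr) reaches the two groups by different routes:

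- **Randomized subjects**, Protocol Table 1, footnote 6: "Safety central laboratory tests including serum creatinine (SCr) and cystatin C", at visits 3 to 10.
- **Observational cohort**, Protocol synopsis and 2.2.1: "No additional blood samples will be taken for study purposes after visit 2". Table 2, footnote 9: "Local laboratory test results will be collected from medical records, including serum creatinine and serum cystatin C (if available"). Footnote 13 allows visits 9 and 10 by phone.

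For AKI-SCr7d, SAP 6.1.2 lists "SCr evaluation visit: baseline, Visit 3, 4, 5, 6, 7 and 8". Table 2 in both documents has no column for visit 6 or 7 in the observational cohort. Protocol Table 8 gives that cohort's biochemistry as "Visits 3-10/EoS", but Section 5.7.4, which introduces Table 8, says local results and "24-hours UO data will be collected, if available at visits according to the Schedule of Assessments" in Table 2.

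**The concern.** The data source is tied to the factor being judged. If unknown status is more common in one NC group, scoring it as no event removes events from that group only, and RR and TPR move for a reason unrelated to the biomarker. Judging NephroCheck is a stated exploratory objective.

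No planned output would show this. The multiple imputation (MI) and missing-as-event analyses in SAP 7.4.1.2 and 7.4.2 cover the randomized efficacy comparison. SAP 7.2.1 tabulates follow-up discontinuation in the NC-negatives, not missing SCr by NC group. SAP 7.11.1 adds nothing for the PFAS.

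The word unknown is also undefined. SAP Table 10 and 7.11.1 refer to Section 6.1 for missing-data handling of the primary and secondary endpoints, but 6.1.1 and 6.1.2 state no rule. The only gloss, in 7.4.1.2 and 7.4.2, is a missing value at any evaluation visit. Carried literally into 7.9.1, it could turn a subject with an observed qualifying value and one missed visit into a non-event.

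AKI-SCr7d has a further problem that arises even when nothing scheduled is missing: the two groups may not share the same visits.

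**Working it through.** **Plan's own figure.** The documents give none for the PFAS. The nearest is the 80% power in SAP Section 4: 60% versus 42%, one-sided 0.05 and 99 per arm after 10% drop-out give 81.7%. That figure reproduces but does not bear on this point.

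**Inputs.** Placebo (NC-positive) AKI risk is 60% (SAP Section 4). The weight is (110 + 110)/110 = 2, so there are 220 weighted positives. The NC-negatives number 440, the Protocol cap. The NC-negative risk of 20% and every missing fraction are assumptions.

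**Formula.** For AKIRisk > 0.3, with missingness unrelated to outcome within group, the scored risk is p(1 − m). Hence RR under the rule = true RR × (1 − m_pos)/(1 − m_neg). The multiplier does not depend on the assumed 20%.

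**True values.** Events are 132 of 220 and 88 of 440. RR = 0.60/0.20 = 3.00; TPR = 132/220 = 60.0%; TNR = 352/(352 + 88) = 80.0%.

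**One row in full: 10% unknown in positives, 20% in negatives.** Scored events are 132 × 0.9 = 118.8 and 88 × 0.8 = 70.4. RR = 0.54/0.16 = 3.38. TPR = 118.8/189.2 = 62.8%. TNR = 369.6/(369.6 + 101.2) = 78.5%. With unknown counted as event, RR = (0.54 + 0.10)/(0.16 + 0.20) = 0.64/0.36 = 1.78.

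| Unknown, NC+ / NC− | RR, SAP rule | TPR | TNR | RR, unknown = event |
|---|---|---|---|---|
| 10% / 10% | 3.00 | 60.0% | 78.1% | 0.64/0.28 = 2.29 |
| 10% / 20% | 3.38 | 62.8% | 78.5% | 1.78 |
| 0% / 20% | 3.75 | 65.2% | 80.8% | 0.60/0.36 = 1.67 |
| 20% / 10% | 2.67 | 57.1% | 75.9% | 0.68/0.28 = 2.43 |

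At 5% unknown in positives and 10% to 40% in negatives, the multiplier runs from 0.95/0.90 = 1.06 to 0.95/0.60 = 1.58.

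**Partial data.** One qualifying value makes a known event. Suppose each of visits 3 to 5 is missing in 20% of NC-negatives, positives are complete, and an event qualifies at k of the three visits. The share of events lost is 0.2^k, so RR = 3/(1 − 0.2^k) = 3.75, 3.13 and 3.02 for k = 1, 2, 3. If AKI persists, little bias remains. The opposite bound is much wider: about 40% are unknown, and RR = 0.60/(0.20 + 0.80 × (1 − 0.8³)) = 0.60/0.5904 = 1.02.

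**Informative missingness.** Suppose 88 NC-negatives are unknown and only 5% of them (4.4) have AKI. The known 352 hold 83.6 events. The SAP rule gives 0.60/(83.6/440) = 3.16. MI that misses the lower risk gives 0.60/(83.6/352) = 2.53. Here the existing rule is closer to 3.00.

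**AKI-SCr7d schedule under Table 2.** Visit 5 is T0 + 72 h, and visit 8 on day 7 is about T0 + 144 h, a gap of 72 h. An NC-negative followed to day 7 therefore has no SCr pair within 48 hours ending after visit 5, and only the 1.5-times-baseline limb can be newly met. With visit 8 on day 5 or 6 the gap is about 24 or 48 h. If 5% or 10% (assumed) of NC-negative events were detectable only through visits 6 and 7, RR would be 0.60/0.19 = 3.16 or 0.60/0.18 = 3.33, carrying the 72-hour risks over to 7 days.

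**The case against.** The analysis is exploratory and the factors are only explored. The rule is disclosed and matches the default for exploratory proportions in SAP 6.1.3. Only 2 of the 23 factors in Table 13 are AKIRisk cut-offs. The Protocol expects at least a week in hospital, so a large share of NC-negatives without usable SCr has no support in the text. For AKI-SCr72h the scheduled visits (3, 4, 5) are the same in both groups, so only source and availability differ. For MAKE, deaths and RRT in the observational cohort are followed to end of study (Protocol 5.5.1), which leaves mainly the eGFR component exposed. All of this stands and limits the weight of the point.

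Three stronger readings are tempting, and the documents do not support them:

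- **That the rule inflates NephroCheck's performance.** No missing fractions are given. Equal fractions leave RR and TPR unchanged, and the reverse pattern lowers them.
- **That MI should replace the rule.** Local SCr may be drawn on clinical need, so missing-at-random is doubtful, and the informative example shows MI can do worse.
- **That visits 6 and 7 are certainly absent in NC-negatives.** Table 8 can be read as including them. Section 5.7.4 points to Table 2, but the conflict is unresolved.

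None of this supplies what is missing: a definition of unknown, its frequency by NC group, or any alternative handling.

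**Conclusion.** The point holds as a gap in an exploratory analysis. A stated rule, followed exactly, can shift the NephroCheck RR and TPR when unknown status differs between groups, and nothing planned for the PFAS would reveal it. In the illustration RR under the rule runs from 2.67 to 3.75 around an assumed 3.00, while TNR moves little. Those figures rest on the assumed 20% risk, the assumed missing fractions and, in the table, missingness unrelated to outcome. The 0% versus 20% row is an extreme case, not an expectation. MAKE is not quantified because no rate for the eGFR component is given.

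The AKI-SCr7d mismatch is separate and depends on which Protocol table describes the data collected. Efficacy conclusions are untouched. This is a cheap improvement, to be considered rather than required.

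**What to change.** In SAP 7.9.1, in this order:

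1. **Visit set.** Reconcile Protocol Tables 2 and 8 on observational SCr at visits 6 and 7. If those visits are not collected, derive AKI-SCr7d for the NC comparison on visits 3, 4, 5 and 8 in both groups. This set must govern the later steps. Otherwise every event-free NC-negative would be unknown for AKI-SCr7d, the event bound would score the whole group as events, and MI would have no observed NC-negative values at visits 6 and 7.
2. **Definition.** Unknown means no observed qualifying SCr, death or RRT (as the endpoint allows) and at least one SCr missing from that visit set. Observed events stay events.
3. **Reporting.** Tabulate the unknown fraction by NC group and endpoint. If it is negligible, the table itself supports the NephroCheck result.
4. **Sensitivity.** Keep the no-event rule as the main analysis. Add an unknown-as-event bound and MI within NC group for RR, TPR and TNR, with neither leading.

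The cost is SAP wording and programming on data already planned; no new collection is needed. The downsides are an event bound that can be very wide, an MI that leans on missing-at-random, and a common-visit analysis that ignores visit 6 and 7 data in the placebo group.

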**Table 13 Potential Risk Factors for Development of AKI and MAKE**

Risk Factor	Classification
Circulatory Shock	0: No 1: Yes
Nephrotoxic Drugs	0: No 1: Yes
Radiocontrast Agents	0: No 1: Yes
Poisonous Plants and Animals	0: No 1: Yes
Dehydration or Volume Depletion	0: No 1: Yes
Advanced Age ( $\geq 70$ years)	0: No 1: Yes
Female Gender	0: No 1: Yes
Black Race	0: No 1: Yes
CKD	0: No 1: Yes
Chronic Diseases (Heart, Lung, Liver)	0: No 1: Yes
Diabetes Mellitus	0: No 1: Yes
Anemia	0: No 1: Yes
Prior AKI	0: No 1: Yes
Left Ventricular Ejection Fraction ( $<40\%$ )	0: No 1: Yes
AKIRisk Score ( $>0.3 \text{ (ng/mL)}^2/1000$ ) [Postsurgery]	0: No 1: Yes
AKIRisk Score ( $>0.7 \text{ (ng/mL)}^2/1000$ ) [Postsurgery]	0: No 1: Yes
Peripheral Arterial Disease	0: No 1: Yes
Use of Intravenous Radio-contrast	0: No 1: Yes
Higher Risk Surgery	0: No 1: Yes
Duration of CPB ( $\geq \text{Median}$ )	0: No 1: Yes
Duration of Aortic Cross-Clamp 1 ( $\geq 0.5$ hours)	0: No 1: Yes
Duration of Aortic Cross-Clamp 2 ( $\geq 1.0$ hours)	0: No 1: Yes
eGFR Based on Serum Creatinine ( $<45 \text{ mL/min/1.73 m}^2$ ) [Baseline]	0: No 1: Yes

CKD: chronic kidney disease; AKI: acute kidney injury; CPB: cardiopulmonary bypass pump; eGFR: estimated glomerular filtration rate

In addition to the above, the following analyses will be conducted for Observational Cohort.

- Primary efficacy endpoint and secondary efficacy endpoints will be summarized for the subjects with NC positive within T0 + 24 hours and NC negative within T0 + 24 hours and all subjects in Observational Cohort. In the table, each stage of AKI-SCr72h and AKI-SCr7d and each individual outcomes of MAKE30/90 will also be summarized.
- For Observational Cohort, the association between MAKE30/MAKE90 (and also each individual outcomes, of all-cause mortality, initiation of RRT and eGFR based on SCr at day 30 (Visit 9)/day 90 (Visit 10) equal to or less than 75% of the baseline value) and primary, secondary and exploratory endpoint of AKI proportion is evaluated by a contingency table. The following endpoints of AKI proportion will be used;
  - AKI-SCr72h (primary endpoint) and each stage,
  - AKI-SCr7d (secondary endpoint) and each stage,
  - AKI-SCr stage 2 or 3 (within 72 hours after T0), and
  - AKI-SCr stage 2 or 3 (within 7 days after T0)

